3.2 Treatment

3.2.1 Waiting Period (Commercial Product Period)

Subjects who enroll in the study while on IV infusions of a commercial immune globulin product and who need to wait for the scheduled start of their IMP treatment will continue on their current product with their usual dose and treatment cycle during the Waiting Period.

Subjects who have been receiving another investigational immune globulin product will be switched to commercially available IGIV product as selected by the Investigator at enrollment in consultation with their treating physician.

Subjects on IGSC therapy before study entry will be switched to commercially available IGIV product as selected by the Investigator at enrollment in consultation with their treating physician.

For any subjects who are switched from IGSC or investigational immune globulin product to a commercial IGIV product, the waiting period on the commercial IGIV will be at least 3 cycles prior to IMP infusion 1.

Any necessary changes in dosage will be determined by the Investigator according to the usual standards of care.

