3.5 Study Duration

3.5.1 Duration of Subject Participation

The Screening Visit will be conducted 21 days (± 2 days) before the Baseline Visit (Infusion 1 IMP, or CP for Subjects in Waiting Period) for subjects on a 21-day cycle, 28 days (± 2 days) before Baseline for subjects on a 28-day cycle, or up to 17 days before the Baseline Visit for subjects receiving IGSC when they enter the study.

To cover seasonal variations, all subjects will be treated with the IMP for approximately 1 year. After the last infusion, AEs will be monitored for 21 days (± 2 days) or 28 days (± 2 days) days, depending on the infusion cycle, and all subjects will then return for a long-term safety visit (LTSV), at Week 51 for subjects on a 21-day cycle and Week 52 for those on a 28-day cycle.

However, the expected total duration of subject participation from enrollment to LTSV will include the Waiting Period on commercial product treatment. This period will vary, depending on the date of enrollment and the start of IMP treatment in the assigned scheduling group.

The safety evaluation phase (including an evaluation at Week 4 for subjects on a 4-week treatment regimen; Week 3 for subjects on a 3-week treatment regimen after the first IMP infusion in 5 subjects and another at Week 4 or 3, depending on treatment regimen, after the first IMP infusion in the next 10 subjects, with the start of IMP treatment at staggered intervals), is expected to be completed by Study Week 36. Thus, if there is no delay in completing the two evaluations, a subject enrolled in the study at the beginning of recruitment and assigned to Group 3 (start of IMP after both evaluations are complete) would have a Waiting Period on commercial product of 36 weeks. The total study duration for this subject would be 88 weeks (approximately 21 months). Subjects who enroll at a later time and are assigned to Group 3 would have a shorter Waiting Period and a correspondingly shorter total study duration.

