5.2 Safety Endpoints

Safety will be evaluated via the following assessments:

- All reported AEs
- Rate (per subject per infusion), severity, and relatedness of AEs
- Frequency of temporally associated AEs
- Infusional AEs
- Assessment of local tolerability to IMP infusions: Reactions at infusion site
- Adverse reactions/suspected adverse reactions
- Vital sign changes, including changes in systolic and diastolic blood pressure, heart rate, respiratory rate, and body temperature
- Changes from Screening in physical examination findings
- Changes from Baseline in laboratory parameters (blood chemistry, hematology, urinalysis, hemolysis, d-dimer, protein S, and protein C concentrations, titers of antibodies to $\beta 2\text{GPI}$ and $\beta 2\text{GPI-DI}$)
- Frequency of clinical signs of hemolysis and/or thrombosis within 72 hours after infusion of the IMP
- IGIV-associated hemolysis
- Changes from Screening in viral safety markers (HAV, HBV, HCV, HIV-1, HIV-2, and B19)
- Comparisons of safety variables during treatment with IMP and during the Waiting Period on commercial product will be made as described in Section 12.3.4.

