Infusion of Current Immunoglobulin Product (if needed)

Subjects treated with commercial IGIV or IGSC may receive their current treatment infusion either before the screening visit or within 1 day after all screening-related laboratory assessments are completed. The first study infusion visit (whether the start of ProMetic IMP or continuation of CP during the Waiting Period) will be scheduled according to the subject's usual treatment cycle. (Subjects on another IGIV or IGSC investigational product at study entry may receive the last administration of that product at screening. They will not be part of the randomization scheme and will be assigned to Group 3 and switched to commercially licensed IGIV selected by the Investigator in consultation with their treating physician. They will continue CP for the duration of the Waiting Period and at a minimum of 3 months in order to satisfy requirement for 3 months on a stable dose of commercial product prior to first IMP infusion.)

Safety Evaluation Phase (Groups 1 and 2)

The safety evaluation phase includes an evaluation of Group 1 and then Group 2. Interim safety testing will be performed prior to the second infusion (at Week 4 in subjects on 28 day cycle, and Week 3 in subjects on 21 day cycle) in five subjects starting IMP treatment at staggered 2-week intervals (Group 1). The results from these 5 subjects are evaluated by the Investigators and the DSMB and submitted to the FDA for review. These subjects will continue on IMP while awaiting review, but no further subjects will be started on IMP. Contingent on FDA and DSMB approval after review of the interim safety results in Group 1, 10 further subjects (Group 2) will receive the first IMP infusion staggered at an interval to be determined by the FDA. The safety evaluation phase continues for Group 2 with interim safety testing as done in Group 1, and the results from these next 10 subjects are evaluated by the Investigators and the DSMB and submitted to the FDA for review. Contingent on FDA and DSMB approval after review of the interim safety testing in Group 2, IMP infusions for the next 60 subjects, including 35 adults (Cohort 1) 25 children (Cohort 2) will start. The starting date of the first IMP infusion in this last group will not be staggered.

7.4 Baseline and IMP/CP Infusion 1

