5.2. Safety Population

The safety analysis set will consist of all subjects who are enrolled into the study and received study treatment (IMP or CP). Safety population will be used in safety analyses.

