6. STATISTICAL ANALYSES

6.1. General Considerations

Descriptive statistics and analyses will be provided by cohort, the age groups within Cohort 2 and, where appropriate, overall (combined all cohorts). Descriptive statistics for continuous variables will include the number of observations, mean, standard deviation (SD), median, minimum, and maximum values. For categorical variables, summary measures will include the number and percentage of subjects in each category.

Individual subject data will be presented in listings by cohort, subject identification number (ID), treatment schedule and, where appropriate, assessment.

All data summaries and tabulations will be prepared by using SAS® Version 9.1 or later.

For the purpose of reporting, subject weights and doses are rounded to zero decimal place.

Safety analyses will be summarized by the CP Treatment Period and by IMP Treatment Period.

Unless specifies otherwise, the efficacy analyses will be presented for all subjects in the all treated population as follows:

- Cohort 1 only
- Cohort 2 only
- Each of the 3 age groups within Cohort 2
- Cohorts 1 and 2 combined

The primary efficacy analysis will be based on the separate analyses for Cohort 1 for adult population and Cohort 2 for pediatric population using all treated population.

Efficacy data will be summarized similarly for CP Treatment Period.

PK analyses will be summarized by 21- or 28-day cycles for the IMP Treatment Period, unless otherwise specified.

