10.2. Secondary Efficacy Endpoints

The following secondary efficacy endpoints for the study will be summarized for the all treated population:

- Number, type and duration of infections other than acute SBIs
- Total serum IgG trough levels
- Episodes of fever ($\geq 100.4^{\circ}\text{C}$)
- Number of days out of work/school/kindergarten/day care or unable to perform normal daily activities due to infection
- Number of days of hospitalization due to infection
- Number of days of antibiotic use for infection prophylaxis and/or treatment

Data listings will also be provided.

Additionally, efficacy endpoints measured during both the CP Treatment Period and the IMP Treatment Period will be summarized side-by-side using the appropriate descriptive statistics using all treated population. For the CP Treatment Period, the summary descriptive statistics will be aggregated over all commercially licensed products.

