11. EVALUATION OF SAFETY PARAMETERS

Evaluation of safety includes the analysis of treatment-emergent adverse events (TEAEs) and the analysis of laboratory investigations.

All TEAEs experienced will be recorded during the study and coded using the Medical Dictionary for Regulatory Activities (MedDRA) version 17.0. Details to be collected include TEAE diagnosis, date and time of onset and resolution, whether the event is ongoing, whether the event is serious, frequency, severity, outcome status, action taken and relationship to study drug (IMP or CP).

Safety endpoints measured during both the CP Treatment Period and the IMP Treatment Period will be summarized side-by-side using the appropriate descriptive statistics.

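### The SAP's CP and IMP columns only partly share the same subjects, so differences in who waited can look like differences between products

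*SAP*

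**What the plan says.** Protocol 5.2, like the synopsis, includes this item in its list of safety endpoints: "Comparisons of safety variables during treatment with IMP and during the Waiting Period on commercial product will be made". The sentence then defers to Section 12.3.4 for the method. That section rules out formal analysis between the two periods and asks for side-by-side descriptive statistics, with all commercial products pooled.

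The SAP follows this. Section 6.1 states: "Safety analyses will be summarized by the CP Treatment Period and by IMP Treatment Period". Section 11 states: "Safety endpoints measured during both the CP Treatment Period and the IMP Treatment Period will be summarized side-by-side using the appropriate descriptive statistics". Section 10.2 does the same for efficacy: "efficacy endpoints measured during both the CP Treatment Period and the IMP Treatment Period will be summarized side-by-side". The safety population in SAP 5.2 is "all subjects who are enrolled into the study and received study treatment (IMP or CP"), and the all treated population in 5.1 has the same definition. Summaries are split by cohort and pediatric age group. The SAP names no table limited to subjects with data in both periods and no within-subject difference. It does not call the columns unpaired; it is silent on pairing.

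Three protocol passages decide who has a CP period:

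- Section 3.2.1, for subjects switched from IGSC or an investigational product: "the waiting period on the commercial IGIV will be at least 3 cycles prior to IMP infusion 1".
- Section 7.3, on what the first study infusion can be: "whether the start of ProMetic IMP or continuation of CP during the Waiting Period".
- Section 3.5.1: "Subjects who enroll at a later time and are assigned to Group 3 would have a shorter Waiting Period".

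**The concern.** CP always comes before IMP in the same person, so a subject who waits can serve as his or her own control. The planned tables do not use this. They set a column of subjects who waited beside a column that also contains subjects who did not. If the two kinds of subject have different underlying rates of adverse events or infections, the columns will differ even when the products behave identically.

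The cohort and age split handles part of any age imbalance. It does not separate waiters from direct starters, or switchers from stable IGIV users. At stake is how a reader interprets the safety and secondary efficacy tables. The efficacy decision does not depend on them.

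**Working it through.** **Is there a figure to reproduce?** No. The documents' only power figures concern the one-sample SBI test, which does not enter here. The documents give neither the number who waited nor any rate by waiting status.

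**Step 1: who is in each column.**

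- *Both columns:* anyone who waited and then received IMP. This includes every switcher who reaches IMP, after at least 3 cycles (9 or 12 weeks) on CP (Protocol 3.2.1 and 7.3).
- *IMP only:* a stable IGIV user whose first study infusion is IMP. Protocol 1.4 dates the clearance of Group 3 at 13 October 2016 (DSMB) and 20 December 2016 (FDA). After that the safety review imposes no wait. Protocol Table 2 allows 12 further weeks of pediatric recruitment beyond the 36-week evaluation phase, so later stable-IGIV children may also start directly.
- *CP only:* a subject who leaves during the wait. The SAP definition admits such a subject; the protocol synopsis requires at least one IMP dose.

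The CP column is thus largely a subset of the IMP column, and the overlap is incomplete in both directions.

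**Step 2: the composition artefact with no product effect.** Let *f* be the share of IMP subjects who waited, *r_w* the percentage of infusions with a temporally associated AE in waiters, and *r_d* that in direct starters. Assume similar numbers of IMP infusions per subject and ignore CP-only subjects.

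- CP column = *r_w*
- IMP column = *f r_w* + (1 − *f*) *r_d*
- CP − IMP = (1 − *f*)(*r_w* − *r_d*)

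With assumed values *r_w* = 30% and *r_d* = 20%:

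| *f* | CP column | IMP column | CP − IMP |
|---|---|---|---|
| 0.4 | 30% | 24% | 6 points |
| 0.6 | 30% | 26% | 4 points |
| 0.8 | 30% | 28% | 2 points |
| 1.0 | 30% | 30% | 0 points |

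If the rates are exchanged (*r_w* = 20%, *r_d* = 30%), the differences become −6, −4, −2 and 0. For a gap of 5 to 15 points and *f* from 0.8 to 0.4, the size runs from 0.2 × 5 = 1 point to 0.6 × 15 = 9 points.

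**Step 3: restrict to subjects with both periods.** Both columns then describe the same people, and the difference is *r_w* − *r_w* = 0 in every row. This removes the composition artefact only.

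**Step 4: choice of measure.** SAP 11.2 reports the percentage of subjects with an event. The longest projected wait is 36 weeks; the IMP period runs to Week 51 or 52. With a constant, identical weekly risk and an assumed 50% of subjects affected over 52 IMP weeks, the CP percentage is 1 − (1 − 0.5)^(*w*/52):

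- *w* = 36 weeks: 38%
- *w* = 12 weeks: 15%

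Limiting the table to common subjects does not cure this. A per-infusion or per-time rate does.

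**The case against.** The strongest reply is that the SAP does what Protocol 12.3.4 asks: descriptive columns, no formal comparison, and no conclusion resting on them. This stands, and it is why the point is minor. It does not make the columns comparable. The comparison remains in the list of safety endpoints, and readers will subtract adjacent columns. The SAP repeats the no-formal-comparison rule only for the primary efficacy endpoint (Section 10.1), not in Section 11.

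Part of the need is already met. Disposition is reported by period, subject listings are provided, SAP 11.1 includes the proportion of infusions affected, and the hemolysis listing in SAP 11.5.1 uses a within-subject reference. None of these shows the same subjects' rates on both products.

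A paired table also remains confounded. The order is fixed and season differs. CP pools several products (nine are named in SAP 9.1). The 7-day post-infusion laboratory tests are scheduled for IMP only (Protocol 6.8 and 6.9). This stands too and must be stated on the table.

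Three stronger readings are tempting but unsupported:

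- *The bias flatters IMP because switchers are concentrated on CP.* The documents give no number of switchers and no event rate for them, and switchers who start IMP count in that column as well. The exposure effect in Step 4 works the other way.
- *Treating the columns as independent gives a wrong error rate.* No test between periods is planned, so there is no error rate to distort.
- *Pairing gains precision.* That depends on the intra-subject correlation. Assume 25% of infusions affected, 5 CP and 15 IMP infusions per subject, and 45 of 75 subjects with both periods. At a correlation of 0.2 the standard error is 3.4 points for all subjects and 3.0 for the paired table. At 0.05 it is 3.21 and 3.25, so nothing is gained.

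**Conclusion.** The point holds at low severity. The CP and IMP columns share only part of their subjects, by rule rather than by accident, and the SAP plans no table on common subjects. Differences in who waited can therefore appear as differences between products.

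The illustrative size is 2 to 6 percentage points. It rests entirely on assumed inputs: a 10-point gap between direct starters and waiters, with 80% to 40% of IMP subjects having waited. The artefact is zero if everyone waited or if the two groups have equal rates, and its sign is unknown. It would go too far to say that the columns hold different people.

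The primary SBI test uses IMP-period data only, and the 40% criterion for infusions with a temporally associated AE is weighted by IMP infusions. Neither is affected.

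**What to change.** In SAP 10.2, 11 and 11.1:

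- Add one descriptive CP/IMP table limited to subjects with at least one study CP infusion and at least one IMP infusion. Define membership by infusions: the SAP defines the CP period as time elapsed from enrollment, which for a direct starter need not contain a scheduled study CP infusion.
- Show the within-subject difference in the percentage of infusions with a temporally associated AE, and in infections other than SBIs per subject-year. Use per-infusion or per-time rates throughout this table, not percentages of subjects.
- Report how many subjects waited, started IMP directly, switched from IGSC or an investigational product, or received CP only.
- Keep the all-subject tables, described as non-comparative summaries.
- Repeat in SAP 11 the statement in Protocol 12.3.4 that no formal comparison is made. The new table needs no test and should not rest on a confidence interval.
- Footnote the remaining confounding: fixed order, season, pooled commercial products, and 7-day post-infusion laboratory tests on IMP only.

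The cost is some SAP wording and a few tables from data already collected. The one drawback is that the comparative table will contain fewer subjects.

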11.1. Temporally Associated TEAEs (TAAEs)

The FDA recommends that for a novel IGIV formulation, a study should demonstrate a TA rate of not more than 40 TAAEs associated with the study drug per 100 administrations. A TAAE should be established as related to the infusion of study drug by implicating temporal association.

For the purpose of this study, TAAEs are considered temporally associated with the study drug infusion if they occur in the period from the start of the infusion until 72 hours after the end of the infusion. The overall TAAE rate considered temporally associated with the study drug infusion and the rate of at least possibly related TAAEs considered temporally associated with the study drug infusion will be considered. A one-sided 95% upper confidence boundary for this percentage will be calculated by using the normal approximation.

The proportion of infusions with a TAAE will be analyzed using a non-inferiority test, with the objective of demonstrating that the percentage of infusions with one or more infusional TAAE is less than 40%. This will be achieved by calculating the percentage of affected infusions for each subject, and then calculating a (weighted) mean of these percentages, with a 95% (one-sided) confidence interval. A suitable transformation will be used if appropriate. The upper limit of this confidence interval should be below 40% in order to demonstrate non-inferiority. Weighting will be based on the number of IMP infusions for which data are available. This method of calculation of the confidence interval takes proper account of the observed intra-subject correlation because it is based on a single summary data point for each subject.

The following SAS code can be used in the analysis.

```
proc genmod data=xxxxxx descending ;  
  class x1 x2 ...label/ ;  
  model resp_dur = / cl dist = bin link = logit alpha=0.1 ;  
  repeated subject = xxx / type=exch ;  
run;
```

TAAE will be summarized by:

- during the infusion (i.e., infusional TEAEs)
- within 1 hour of infusion
- within 4 hours of infusion
- within 24 hours of infusion
- within 72 hours of infusion

A summary of descriptive statistics will be provided for the IMP subjects in the safety population.

The following observations will be summarized using the standard set of summary statistics.

- Summary of TAAEs by infusion rate;
- Total number of TAAEs and infusional TEAEs;
- The number and proportion of infusions with which one or more TAAEs and infusional TEAEs are associated;
- The number of temporally associated TAAEs and infusional TEAEs per infusion;
- Number of infusions/subject where infusion rate was decreased due to an AE, and
- Subjects with at least one infusion where rate was decreased due to an AE

The operational definition of adverse reaction/suspected adverse reaction for analysis purposes will be all AEs meeting any of the following criteria:

- (a) The event began during or within 72 hours following the last IMP infusion;
- (b) The event was considered by the investigator and/or the sponsor to be at least possibly related to the IMP administration; or
- (c) The causality assessment was missing or indeterminate.

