10.1.3 Infusional and Temporally Associated Adverse Events

AEs that occur during the infusion of the IMP or CP will be recorded as Infusional AEs. Temporally associated AEs are those that occur during the infusion or within 72 hours following the end of the infusion, regardless of other factors that may impact a possible causal association with IMP/CP administration.

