The FDA recommends that for a novel IGIV formulation, a study should demonstrate that an upper 95% confidence limit on the rate of infusions having one or more temporally-associated AEs be less than 40 infusions per 100 patient infusions (0.40). An AE should be established as associated to the infusion of study drug by implicating temporal association (this includes all AEs regardless of relationship to product).

For the purpose of this study, AEs are considered temporally associated with the study drug infusion, if they occur in the period from the start of the infusion until 72 hours after the end of the infusion. To meet the recommended target for this safety endpoint, the number of infusions having one or more temporally-associated AEs will be analyzed using a negative binomial regression model with an over-dispersion parameter to account for possible intra-patient correlation and the number of infusions per patient as an offset variable. To calculate the required upper 95% confidence limit, an intercept-only negative binomial regression model will be fit to the data in which the response for each subject is the number of affected infusions (i.e., the number of infusions with one or more temporally-associated AEs). A two-sided 90% confidence limit on the intercept will then be computed on the inverse link scale to achieve an upper one-sided 95% confidence limit on the expected mean number of infusions per 100 patient infusions having one or more temporally associated AEs. This upper limit should be below 40 in order to demonstrate safety with respect to the infusion process.

Adverse Reaction/Suspected Adverse Reaction

The operational definition of adverse reaction/suspected adverse reaction for analysis purposes will be all AEs meeting any of the following criteria: (a) the event began during or within 72 hours following the last IMP infusion; (b) the event was considered by the

investigator and/or the sponsor to be at least possibly related to the IMP administration;
or (c) the causality assessment was missing or indeterminate.

β2GPI and to β2GPI-DI Antibody Data

Data on formation of antibodies to β2GPI and to β2GPI-DI will be tabulated and discussed individually in the text.

Viral Safety Data

Viral safety data will also be listed (not tabulated) and any seroconversions will be discussed individually in the text.

Hemolysis Data

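### In SAP 11.1 the 40% temporally associated AE test has a fixed threshold, level and estimator, but its objective names a narrower event, its scale is left open, and its text and code describe different procedures

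*SAP*

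**What the plan says.** **Protocol.** Section 12.3.4 counts an infusion as affected if any AE, whatever its cause, starts between the beginning of the infusion and 72 hours after its end. Then "the number of infusions having one or more temporally-associated AEs will be analyzed using a negative binomial regression model", with the number of infusions as offset. The one-sided 95% upper limit, taken from a two-sided 90% interval, must be below 40 per 100 infusions.

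**SAP 11.1, event.** AEs are temporally associated "if they occur in the period from the start of the infusion until 72 hours after the end of the infusion". The test, however, is set up "with the objective of demonstrating that the percentage of infusions with one or more infusional TAAE is less than 40" per cent. Protocol 10.1.3 says "AEs that occur during the infusion of the IMP or CP will be recorded as Infusional AEs", and the SAP's own list of time windows has "during the infusion (i.e., infusional TEAEs" as its first entry.

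**SAP 11.1, method.** The percentage of affected infusions is computed for each subject and averaged, with a one-sided 95% interval whose upper limit must be below 40%. "Weighting will be based on the number of IMP infusions for which data are available". Between the averaging and the decision sentence stands "A suitable transformation will be used if appropriate". The paragraph before it also says "A one-sided 95% upper confidence boundary for this percentage will be calculated by using the normal approximation". The example code fits a binomial logit model with an exchangeable repeated-subject structure and alpha 0.1.

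**The concern.** This is the only safety endpoint with a statistical pass criterion, in an open-label single-arm trial. Three things in the SAP text could let the pass statement differ from what Protocol 12.3.4 promised:

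1. The objective names a subset of the endpoint. An infusion with an AE during it is always an infusion with an AE by 72 hours, but not the reverse, so the percentage tested can only be equal or lower.
2. The scale on which subject percentages are averaged can be picked after the data are seen, with no trigger stated.
3. A programmer following the text and a programmer following the code would run different procedures, and neither would run the protocol's.

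**Working it through.** **The plan's own figure.** The documents give no sample size or power for this criterion; the only figure to reproduce is the level. A two-sided 90% limit uses z = 1.645, which is the one-sided 95% quantile. The SAP code's alpha of 0.1 gives the same. Protocol and SAP agree on the level and on the 40% threshold.

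**Inputs from the documents.** About 50 subjects in Cohort 1, 25 in Cohort 2 and 75 in all; 13 infusions (28-day cycle) or 17 (21-day cycle) per subject.

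**Assumed inputs.** Half the subjects on each cycle; intra-subject correlation (ICC) of 0.1, 0.2 or 0.3; true affected-infusion rate p of 40%, 33% or 25%. Subject probabilities are Beta with mean p and the given ICC, and affected infusions y_i are Binomial(n_i, probability).

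**Limits compared** (pass if the limit is below 40%):
- Weighted mean: m = Σ n_i(y_i/n_i) / Σ n_i; limit m + t(0.95, N−1) × SE, with SE from the between-subject spread.
- Subject logits: the same limit on log[(y_i+0.5)/(n_i−y_i+0.5)], back-transformed.
- Subject arcsines: the same limit on arcsin√(y_i/n_i), back-transformed.
- GEE-type: overall proportion, robust SE on the logit scale, z = 1.645.
- Overall logit: as GEE-type, with t(N−1).
- Negative binomial: offset log n_i, limit exp(b + 1.645 SE).

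**False passes (%) at a true 40%, nominal 5%**, 4,000 trials per cell, ICC 0.1 / 0.2 / 0.3. Simulation error near 5% is √(0.05 × 0.95 / 4000), about 0.3 points.

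| Limit | N=50 | N=75 |
|---|---|---|
| Weighted mean | 5.5 / 5.8 / 5.3 | 4.9 / 5.4 / 5.4 |
| GEE-type | 5.6 / 5.8 / 5.0 | 4.9 / 5.3 / 5.3 |
| Overall logit | 5.0 / 5.3 / 4.4 | 4.8 / 5.0 / 4.9 |
| Negative binomial | 4.7 / 3.9 / 2.7 | 4.2 / 3.7 / 2.9 |
| Subject logits | 9.6 / 13.7 / 16.6 | 10.7 / 15.2 / 18.5 |
| Subject arcsines | 9.9 / 12.6 / 14.5 | 10.8 / 13.6 / 15.5 |

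The excess comes from a change of target. At a true 40% and N=50, the back-transformed mean of subject logits averages about 39% (ICC 0.1) and 37% (ICC 0.3), so its limit no longer bounds the percentage of infusions. Transforming the overall proportion does not have this problem.

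A separate simulation (500 trials per setting, N = 20, 40 or 60, ICC 0.1 or 0.3, with the exchangeable GEE fitted directly) gave 5.0–7.0% for the weighted mean, 4.4–6.0% for the GEE, 2.4–5.2% for the negative binomial, 8.0–19.2% for subject logits and 7.8–17.2% for subject arcsines.

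**Below the threshold** (2,000 trials per setting). At a true 33%, the weighted mean passes in 53.8–92.1% of trials, the negative binomial in 39.4–90.4% and subject logits in 78.4–96.9%. The loss from the negative binomial against the weighted mean runs from 92.1 − 90.4 = 1.7 points (N=75, ICC 0.1) to 53.8 − 39.4 = 14.4 (N=50, ICC 0.3). At a true 25% the lowest pass rate is 95.4% (negative binomial, N=50, ICC 0.3), against 98.6% for the weighted mean.

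**Cohort 2 alone** (N=25, ICC 0.3, true 25%). The weighted mean passes in about 86% of trials and the negative binomial in about 72%, a gap of 14 points; another run gave 84% and 72%, a gap of 12. The gap is about 13 points.

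**The case against.** The strongest reply is that SAP 11.1 already has a decision rule. It states the threshold, the level, a mean of subject percentages, the weights, and a decision sentence tied to that interval. That stands. A reader might infer that no rule is fixed at all, and the text does not support this.

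A reader might also take the normal-approximation bound for a rival decision rule computed on pooled infusions, which would ignore clustering. The documents do not say so. The bound follows the two rates that the SAP will consider and has no threshold attached, and the decision interval is said to rest on one summary value per subject. Its unstated role is an editorial matter.

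On *infusional*: the same sentence opens with infusions having a TAAE, which is defined to 72 hours, and the 72-hour proportion is tabulated anyway. A slip is the likely explanation, and nothing shows an intention to test only events during the infusion. The word still sits in the objective of the test.

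On the change of model: the SAP does say that its method allows for intra-subject correlation, and by the figures above the weighted mean holds close to 5%. The change is not harmful in itself. What is missing is a statement that it departs from Protocol 12.3.4; the revision history gives only a general reason for V2.0.

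On the transformation: the SAP names no subject-level scale, and the only scale in its code is a population-level logit, which holds the level. The subject-logit and arcsine figures are therefore the unfavourable end of what the sentence allows. But it comes straight after the averaging of subject percentages, so transforming those percentages is a natural reading.

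**Conclusion.** The concern holds as three repairable defects in a rule that is otherwise stated.

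- **Event.** The literal objective is a subset of the 72-hour endpoint and easier to pass. The documents give no split of AEs by time window, so the effect cannot be sized.
- **Open scale.** This is the one with a demonstrable error-rate cost: about 9 to 19% false passes at a true 40% if subject percentages are transformed, against about 5 to 6% untransformed (N=50 or 75).
- **Text against code.** The weighted mean and the GEE perform almost alike, so the mismatch is mainly one of specification. The protocol's negative binomial is conservative, at 2.7 to 4.7%.

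All figures rest on the assumed correlation, the even split of cycles and the beta-binomial model. At N=50 or 75 the choice matters near the threshold and little at a true 25%. That reassurance does not carry over to Cohort 2 alone, where at a true 25% and correlation 0.3 the choice of limit moves the pass rate by about 13 points.

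**What to change.** In SAP 11.1:

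1. Delete *infusional*, so that the criterion is infusions with at least one AE from infusion start to 72 hours after its end, regardless of causality.
2. Delete the transformation sentence, or allow only a pre-specified transformation of the overall proportion.
3. Name one cluster-aware one-sided 95% upper limit as the decision rule: the untransformed infusion-weighted mean, the exchangeable GEE, or the protocol's negative binomial with infusion offset. Make the text and the example code agree. If the choice is not the negative binomial, note the departure from Protocol 12.3.4 and the reason.
4. Editorial: label the normal-approximation bound as descriptive.

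The cost is SAP wording only; no data collection changes. Keeping the weighted mean or the GEE costs nothing in pass rate. Keeping the negative binomial gives up about 2 to 14 points at a true 33% and 0 to 3 points at a true 25% for N=50 or 75, and about 13 points for Cohort 2 at a true 25% with correlation 0.3.
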